
#### Attachments

Attach Type	File Name
Advertising	INCREASE_flyer_Version_3.pdf
Advertising	INCREASE Recruitment Letter Version 5 CLEAN.pdf

**Informed Consent Process:** Describe the consent/assent procedures to be followed, the circumstances under which consent will be sought and obtained, the timing of obtaining informed consent, whether there is any waiting period between informing the prospective subject and obtaining consent, who will seek consent (Note: all individuals authorized to obtain informed consent should be designated as such in the E-IRB "Study Personnel" section of this application), steps taken to minimize the possibility of coercion or undue influence, the method used for documenting consent, and if applicable who is authorized to provide permission or consent on behalf of the subject. Describe, if applicable, use of specific instruments or techniques to assess and confirm potential subjects' understanding of the nature of the elements of informed consent (i.e., research involving adult subjects with impaired consent capacity) and/or a description of other written materials that will be provided to participants or legally authorized representatives. If you have a script, please prepare it using the informed consent template as a guide, and submit it on a separate page. For additional information, see the "Informed Consent Standard Operating Procedures (SOPs)" [[PDF](#)].

#### *Informed Consent for Research Involving Emancipated Individuals*

If you plan to enroll some or all prospective subjects as emancipated, consult with UK legal counsel **when preparing the IRB application and prior to submitting the application to the IRB**. Include legal counsel's recommendations (legal counsel's recommendations may be attached in the E-IRB "Additional Information" section as a separate document, if necessary). For a complete definition of emancipated minors, see the section on *Emancipated Individuals* in the Informed Consent SOP [[PDF](#)].

#### *Informed Consent for Research Involving Non-English Speaking Subjects*

If you are recruiting non-English speaking subjects, the method by which consent is obtained should be in language in which the subject is proficient. Describe the process for obtaining informed consent from prospective subjects in their respective language (or the legally authorized representative's respective language). In order to ensure that individuals are appropriately informed about the study when English is their second-language, describe a plan for evaluating the level of English comprehension, and the threshold for providing a translation, or explain why an evaluation would not be necessary. For additional information on inclusion of non-English speaking subjects, or subjects from a foreign culture, see [Instructions for Recruiting Non-English Speaking Participants or Participants from a Foreign Culture](#).

#### *Research Repositories*

If the purpose of this submission is to establish a research repository describe the informed consent process. For guidance regarding consent issues, process approaches, and sample language see the "University of Kentucky Issues to be Addressed and Sample Consent Language for Tissue/Specimen Repositories or Individual Studies Banking Material for Future Use" [[PDF](#)].

Prior to entering the study, the risks and benefits of participating will be explained to the participant by a member of the study team authorized to obtain informed consent. A signed and dated informed consent form will be retained by the investigator. The study participant will receive a copy of the informed consent form.

[Back to Top](#)

**Research Procedures:** Describe the research procedures that will be followed. Identify all procedures that will be carried out with each group of subjects. Differentiate between procedures that involve standard/routine clinical care and those that will be performed specifically for this research project.

Screening Visit (Week -5 ± 2): Subject appropriateness and safety for the study will be assessed with thorough review of medical history, medication review, physical/neurological exam, vital signs, and ECG. SF-36 will assess pre- study perceived health status. Lifestyle Factor Questionnaire will further assess health history and current health status. A Baseline Questionnaire will assess motivation for participating and understanding of medications. Aβ-PET will be performed to allow stratification at baseline. Approximately 4 hours. Baseline and EOS visit (Scopolamine-challenge; week -4 ± 1 & week 52 ± 1): Subject will apply scopolamine patch at ~8pm the night before this visit to ensure adequate plasma levels of scopolamine. Study partner will drive subject to and from appointment. Medical history and medication review will be performed to ensure no changes have occurred since prior visit. Vital signs will be obtained. Cognitive testing including TMTB, MoCA, CVLT will be performed. Following cognitive testing, subject will remove scopolamine patch. Baseline and EOS visit (Non-challenge; week 0 ± 1 & week 56 ± 1): Medical history and medication review will be performed to ensure no changes have occurred since prior visit. Vital signs will be obtained. Cognitive testing including TMTB, MoCA, and CVLT will be performed. MTM intervention vs. placebo distribution of educational materials on PIM use will be performed. SF-36, Lifestyle Factors Questionnaire, and End of Study (EOS) Questionnaire will be administered at the EOS visit to assess changes in health status. Month 3 & 9 visits (week 13 ± 1 & week 39 ± 1): Telephone check to screen for adverse effects, update medical history and medication review. Month 6 visit (week 26 ± 1): Medical history and medication review will be performed to ensure no changes have occurred since prior visit. Vital signs will be obtained MTM intervention vs. placebo distribution of educational materials on PIM use will be performed. Randomization: For randomization, subjects will be stratified by Aβ positivity on PET scans; if age, gender, education, NART scores, and the number of targeted inappropriate medications using 2015 Beers Criteria are unbalanced between groups after randomization, they will be included in the analyses. Blinding: As the intervention is educational in nature, complete blinding of intervention is not possible. However, we will take the following steps in order to minimize potential bias and achieve the maximum level of blinding possible by this design: 1. When reviewing the medication list prior to the intervention, the coordinator, study pharmacist, and physician will be unaware of the group allocation. 2. Data analysis will be blinded to the intervention.

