We plan to enroll 90 participants. Eligibility and inclusion/exclusion criteria have been selected on the basis of efficacy endpoints and safety concerns and contraindications to scopolamine therapy or PET scanning to minimize the potential for adverse events. Recognized contraindications and medical conditions preventing the use of scopolamine patches or those requiring dosage adjustments will be screened for and subjects excluded from the protocol. Inclusion Criteria: 1. 65 years and older 2. Non-demented 3. No previous reaction or contraindication to scopolamine patch, or medical condition warranting dose adjustment in scopolamine including but not limited to: open angle glaucoma, gastrointestinal or urinary outlet obstructions, seizures, or psychosis. 4. No contraindications to A $\beta$ -PET scan including hypersensitivity to PET ligand or radiation exposures in the past year that would exceed the acceptable safe annual exposure in combination with the A $\beta$  PET 5. Medically stable and able to complete all study activities, as determined by the investigator 6. Reporting at least one potentially inappropriate medication as listed in the Beers 2015 criteria 7. Living in the community 8. Able to identify a study partner who will drive the participant to and from the scopolamine-challenged visits. 9. Willing to participate in this intervention study. Exclusion Criteria: 1. Allergy or other known intolerance to scopolamine patches 2. Narrow-angle glaucoma 3. Difficulty swallowing 4. Stomach or bowel problems (e.g., blockage, muscle weakness, ulcerative colitis) 5. Bleeding 6. Myasthenia gravis 7. Blockage of the urinary tract. 8. Seizures 9. Psychosis

Attachments

**Subject Recruitment Methods & Privacy:** Describe plans for the identification and recruitment of subjects, including how the population will be identified, and how initial contact will be made with potential subjects by those having legitimate access to the subjects’ identity and the subjects’ information. Describe the setting in which an individual will be interacting with an investigator. If applicable, describe proposed outreach programs for recruiting women and minorities as participants in clinical research.

Please note: Based upon both legal and ethical concerns, the UK Medical Institutional Review Board (IRB) will not approve finder’s fees for research studies.

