Physical and neurological examinations, neuropsychological tests, and social and medical histories will be collected: Minimal physical, psychological, social, legal and other risks are associated with these procedures. However, the availability of health professionals, including an experienced dementia care clinical coordinator/neuropsychologist and the ready availability of two on-site social workers to work with patients and families throughout the clinical and research process further minimizes possible risks. Such risks by category include: • Memory and thinking testing: anxiety, stress or boredom • Social Risks: Breach of confidentiality could impact insurability, employability, reproduction plans, family relationships, immigration status, paternity suits, or result in stigmatization. • Psychological Risks: If information is disclosed, anxiety and stress may result from the impact of learning results. Additionally, the risk of psychological stress may exist for family members as well. Scopolamine challenge: Specific adverse events of concern regarding the scopolamine challenge include those associated with the use of anticholinergics in the elderly, including disorientation, confusion, and dizziness. Prior to baseline scopolamine challenge, medical history, concomitant medications, physical and neurologic exams, ECG will be performed to evaluate for potential unforeseen medical risks. The study physician will be responsible for determining if the subject is acceptable for randomization and scopolamine challenge. Subjects will be advised that the scopolamine patch may cause such effects and that they should avoid driving and operating heavy or otherwise dangerous machinery until off the patch for at least 24 hours. Study physicians are available 24-7 should any participant experience adverse side effects. Subjects are advised to have a study partner to drive and accompany them to and from the two study visits during which the scopolamine-challenge will occur. Aβ-PET: Florbetapir F 18 Injection is approved by the United States Food and Drug Administration (FDA) to estimate amyloid neuritic plaque density in adult patients with cognitive impairment who are being evaluated for Alzheimer's disease

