a. Recruitment and Informed Consent: The study investigators will obtain Institutional Review Board (IRB) Approval for all proposed activities and IRB assurances have been filed with the Department of Health and Human Services. b. Assessment of Capacity: Our protocol includes capacity evaluation for all research subjects irrespective of cognitive status to ensure willingness to participate in the research which is performed by our trained licensed clinicians and recorded in our UK-specific research data collection for the proposed project for all subjects recruited from the ADC cohort. Subjects recruited from external sources including the Voter registration list, have not previously undergone capacity assessment. As such, we will require the mandatory use of the University of California, San Diego Brief Assessment of Capacity to Consent (UBACC) by the consenting staff member for all subjects enrolled. Subjects lacking capacity, will not be enrolled in the study, as their understanding and compliance with the medication management intervention is a critical part of the current study. c. Biobanking of A $\beta$ -PET: Biobanking of PET images will be required of all research subjects. This provides for sharing of de-identified images (as well as phenotypic) data with any investigators for the purpose of advancing research in the area of aging and dementia. This will be broadly defined in our consent to allow maximal use of these samples to further research in the field. The biobanking protocol will have no pre-specified time limit and images will be retained indefinitely unless they are withdrawn at the request of the study participant. d. Protections against Risk: The confidentiality of our research subjects will continue to receive high priority. Hard copies of data will be maintained in locked files with access only to key individuals. All information collected on human subjects will be stored in the ADC master database with access to this data strictly monitored. The research part of the database is referenced only by subject code numbers. We appreciate the confidence that our subjects place in us through their participation in our programs. Guaranteeing the privacy of subject records will continue to be an essential function for all personnel involved with this data. Procedures utilized as a part of our research, e.g., cognitive testing, should not require medical or professional intervention. The Inclusion/Exclusion criteria is specifically designed to minimize risk for the scopolamine challenge and A $\beta$ -PET scan. We do not anticipate SAEs in relation to the current protocol or interventions. However, our physicians and professional staff will be available if a problem is identified. e. Staff Qualifications, Training, and Certifications in Human Subjects Research: We will keep private all research records that identify participants to the extent allowed by law. Information obtained from the participant will be combined with information from other people taking part in the study. When we write about the study to share it with other researchers, we will write about the combined information we have gathered. The participant will not be personally identified in these written materials. Provisions to guard against the potential risks and discomforts discussed in section 9 are as follows: Every precaution to prevent a direct study injury will be taken by medical personnel and the investigators. The research participant will be followed by physicians, physician assistants, registered nurses, pharmacists, and other research staff members for the duration of the individual's participation in the research study. Routine care will be provided by the hospital staff. Emergency medical equipment, medications and supplies will be at the physician's disposal should the participants have an acute untoward reaction. The participants will be monitored for clinical adverse experiences throughout study therapy. Throughout the study, all adverse events will be monitored and recorded.

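### The week-52 scopolamine patch goes on the evening before the visit that reviews history and medications, and the supplied text sets no time before it for a physician's clearance

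*Protocol*

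**What the plan says.** **Sequence.** Research Procedures gives one description for both challenge visits (week -4 ± 1 and week 52 ± 1). On the patch: "Subject will apply scopolamine patch at ~8pm the night before this visit to ensure adequate plasma levels of scopolamine". On the review at the visit: "Medical history and medication review will be performed to ensure no changes have occurred since prior visit". The patch comes off after cognitive testing.

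**Safeguard before the first patch.** Potential Risks states: "Prior to baseline scopolamine challenge, medical history, concomitant medications, physical and neurologic exams, ECG will be performed to evaluate for potential unforeseen medical risks". Research Procedures places these assessments at screening (week -5 ± 2).

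**Physician's role.** The next sentence in Potential Risks reads: "The study physician will be responsible for determining if the subject is acceptable for randomization and scopolamine challenge". It is not expressly limited to baseline, and it gives no time.

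**Between the patches.** History and medications are reviewed at week 0 and month 6, and at months 3 and 9 by telephone: "Telephone check to screen for adverse effects, update medical history and medication review". Safety Precautions adds that adverse events are recorded throughout. Study Design plans a physical and neurologic examination at study completion but does not place it before the second patch.

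**Entry criteria.** Safety Precautions relies on them: "The Inclusion/Exclusion criteria is specifically designed to minimize risk for the scopolamine challenge". Inclusion criterion 3 (Study Population) requires: "No previous reaction or contraindication to scopolamine patch, or medical condition warranting dose adjustment in scopolamine including but not limited to" a list of conditions such as urinary or gastrointestinal obstruction, seizures and psychosis.

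**Not supplied.** Data Collection and the study-drug section refer to a schedule table, a study-procedures file and a study-drug file.

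**The concern.** A review meant to catch changes since the last contact protects the participant only if it comes before the exposure. At week 52, as written, it comes the morning after. Staff would learn of a new contraindication when the participant is already wearing the patch.

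The entry criteria describe the participant at screening. Over the following year someone aged 65 or older may develop a condition that criterion 3 or the exclusion list names. In the intervention arm, medication changes are expected by design. A participant may also have reacted badly to the first patch. That would be on file, but no step in the supplied text links the file to a decision about the second patch.

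What is at stake is avoidable exposure of an older person to an anticholinergic drug. Potential Risks itself names disorientation, confusion and dizziness as the effects of concern.

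**Working it through.** The plan states no figure to reproduce. The check compares the two challenges and does calendar arithmetic on the visit windows in Research Procedures.

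**Inputs (weeks).** Screening -5 ± 2, so -7 to -3. First challenge visit -4 ± 1, so -5 to -3. Month 6 visit 26 ± 1, so 25 to 27. Month 9 call 39 ± 1, so 38 to 40. Second challenge visit 52 ± 1, so 51 to 53.

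**Formula.** Nominal gap = later week minus earlier week. Shortest = earliest later date minus latest earlier date. Longest = latest later date minus earliest earlier date.

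| Gap | Nominal | Shortest | Longest |
|---|---|---|---|
| Screening to first challenge visit | -4 - (-5) = 1 | 0 (windows overlap) | -3 - (-7) = 4 |
| Month 9 call to second challenge visit | 52 - 39 = 13 | 51 - 40 = 11 | 53 - 38 = 15 |
| Month 6 visit (last in person) to second challenge visit | 52 - 26 = 26 | 51 - 27 = 24 | 53 - 25 = 28 |
| Screening ECG and exam to second challenge visit | 52 - (-5) = 57 | 51 - (-3) = 54 | 53 - (-7) = 60 |

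The patch goes on one day before the visit. The gap from the month 9 call to the second patch is therefore 13 × 7 - 1 = 90 days, range 11 × 7 - 1 = 76 to 15 × 7 - 1 = 104.

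**Time on the patch before the review.** The visit's clock time is not given. If it starts between 8 am and noon (assumption), the patch has been on for 12 to 16 hours.

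**Side by side.**

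| | First patch | Second patch |
|---|---|---|
| Evaluation stated before the patch | History, medications, exams, ECG | None stated |
| Last scheduled history and medication check before the patch | Screening, nominally 1 week before the visit | Month 9 call, nominally 13 weeks before the visit |
| Physician's decision | Read with the evaluation stated just before it | Duty arguably applies; no time given |
| Visit-day review | After the patch is on | After the patch is on |

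The order within the visit is the same both times. Only the first challenge has a stated safeguard ahead of it.

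**Number affected.** Everyone who reaches week 52, at most the 90 planned. The documents give no rate of new contraindications or of reactions, so none is computed.

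**The case against.** The strongest reply has three parts.

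1. **The duty is already assigned.** The physician must judge acceptability for the scopolamine challenge, and Potential Risks speaks of two challenge visits. A reader might infer that nobody is responsible for clearing the second patch. The text does not support that: the duty can be read to cover both. What stands is that no time is fixed before the second patch, and no information is named as the basis for the decision.

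2. **The missing step may be in the unseen files.** The protocol is an institutional review form that leaves operational detail to attachments. The last in-person visit before week 52 is at month 6, and the text does not say how the participant receives the second patch. That arrangement could include a check. This stands, and it limits the point to the supplied text.

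3. **Much of the risk is already covered.** Four scheduled history reviews fall between the patches (weeks 0, 13, 26 and 39), adverse events are recorded, and participants reaching week 52 will generally have worn a patch before. Physicians are on call at all hours, and the patch is removed after testing. So a reaction to the first patch, and most conditions arising by month 9, should be known. What stays wholly unknown is a condition arising in the last 11 to 15 weeks that nobody reported. The reply reduces the size of the problem but does not remove it. On-call cover acts after exposure, and a safety board that meets twice a year does not clear individual participants.

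A reader might also infer that criterion 3 bars anyone with cognitive effects from the first patch. The criterion is an entry rule and does not define a reaction. A transient cognitive effect is what the challenge is designed to measure.

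**Conclusion.** The point holds as a modest safety gap in the supplied text. At week 52 the stated order puts the review after the exposure. The last scheduled check is 13 weeks earlier (range 11 to 15), and no step before the second patch is named for the physician's decision. The change is worth making because the order defeats the review's own purpose and the remedy is cheap.

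The conclusion rests on reading the visit description literally and on the unsupplied attachments not already containing the step. If they do, a cross-reference is enough.

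Two stronger readings are not supported. One is that participants will often be harmed: the documents give no rate, and the frequency is unknown. The other is that the sequence biases the CRCS comparison: the same order applies in both arms, and nothing in the text shows a distortion of the outcome.

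**What to change.** **Research Procedures.** Add a telephone review of history and medications within 7 days before the week-52 patch. Keep the visit-day review, because a medication change in the last days could affect challenged test performance and should be recorded.

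**Potential Risks.** State that the study physician confirms acceptability before the second patch as well as the first. The basis is the call, the adverse-event record from the first patch, and the scopolamine criteria in Study Population.

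**Rule for withholding.** Withhold the second patch for a new contraindication, or for a reaction to the first patch that the physician judges clinically significant. Do not withhold it for the expected transient cognitive effect. Participants not cleared skip only the week-52 challenged test and stay in follow-up for the Medication Appropriateness Index (MAI), SF-36 and the week-56 unchallenged tests.

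**Gain.** The interval from the last history and medication check to the second patch falls from about 90 days to at most 7. The call does not repeat the exams or ECG.

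**Staff cost (assumed times).** At 20 minutes per call, 90 × 20/60 = 30 hours. At 5 minutes per confirmation, 90 × 5/60 = 7.5 physician hours.

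**Cost to the analysis.** Anyone not cleared has no change in CRCS, which is a primary outcome. If k of 90 are lost, evenly across arms and with no other loss, the standard error is multiplied by √(90/(90 - k)). The values of k are assumed:

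- k = 1: √(90/89) = 1.006, up 0.6%
- k = 5: √(90/85) = 1.029, up 2.9%
- k = 9: √(90/81) = 1.054, up 5.4%

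These figures understate the cost if loss is not random. The decision comes after allocation, and participants who react strongly may be those with the least reserve, so selection bias is possible. The narrow withholding rule is meant to limit it.

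**Optional.** Use a physician unaware of allocation where possible, since the stated protection covers only the period before the intervention: "When reviewing the medication list prior to the intervention, the coordinator, study pharmacist, and physician will be unaware of the group allocation". Report the number not cleared, with reasons, by arm. Say in the SAP how their missing change in CRCS will be handled.
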